### 1 INTRODUCTION

The study is a randomized, double-blind, multicenter, placebo-controlled, flexible-dose (36, 45 or 54 mg/day), 2-arm, (1:1) parallel group study to evaluate the safety and efficacy of SPN-810 (molindone extended release tablets) for reducing impulsive aggression in adolescents (12-17 years of age) with ADHD as an adjunctive treatment to an approved ADHD medication.

#### 2 STUDY OBJECTIVES

The primary objective of this study is to assess the efficacy and safety of flexible doses of SPN-810 (36 to 54 mg/day) in the improvement of IA behaviors in adolescents diagnosed with ADHD when taken in conjunction with standard ADHD treatment.

The key secondary objectives, additional secondary objectives and exploratory objectives are to assess the effect of SPN-810 on the key secondary endpoints, additional secondary endpoints and safety endpoints described below.

### 3 STUDY ENDPOINTS

# **3.1** Primary efficacy endpoint

The primary efficacy endpoint is the percent change (PCHT) in the frequency (unweighted score) of IA behaviors per 7 days in the Treatment Phase (titration + maintenance) relative to the Baseline period calculated over the number of days with non-missing IA diary data.

# **3.2** Key Secondary Endpoints

The key secondary endpoints include the following:

- 1. Investigator-rated Clinical Global Impression Severity Scale (CGI-S)
- 2. Retrospective Overt Modified Aggression Scale (R-MOAS)
- 3. Percent of children whose IA behaviors were remitted at the end of the study measured by R-MOAS score  $\leq 10$ .

### **3.3** Additional Secondary Endpoints

The additional secondary endpoints include the following:

- 1. Investigator-rated Clinical Global Improvement (CGI-I) scale.
- 2. Caregiver-rated CGI-I scale.
- 3. Caregiver-rated CGI-S scale.
- 4. Swanson, Nolan, and Pelham Rating Scale (SNAP-IV) rating scale
- 5. Child Health Questionnaire Parent Form 28 (CHQ-PF28) rating scale
- 6. Stress Index for Parents of Adolescents (SIPA) rating scale

## **3.4** Safety Endpoints

- 1. Incidence of Adverse Events
- 2. Incident of Extrapyramidal Symptoms (EPS)

- 3. Clinical laboratory evaluations
- 4. Vital signs and ECG
- 5. Suicidal symptoms (C-SSRS)
- 6. Infrequent behaviors

### 4 STUDY METHODS

# **4.1** Study Design

This study is a randomized, double-blind, multicenter, placebo-controlled, flexible-dose (36, 45 or 54 mg/day), 2-arm, (1:1) parallel group study to evaluate the safety and efficacy of SPN-810 (molindone extended release tablets) for reducing impulsive aggression in adolescents (12-17 years of age) with ADHD as an adjunctive treatment to an approved ADHD medication. Schedule of Visits and Procedures.

All subjects who are consented are required to follow the protocol procedures regardless of the number of doses of SM taken. The Schedule of Visits and Procedures are presented in Table 1.

#### **Table 1 Schedule of Events and Assessments**

Phase	Pre-Tre	atment	Treatment			Conversion/Tap		
Period	Screening	Baseline	Titration		Maintenance			er
VISIT NUMBER	1	2	3	4	5	6	7	8 (EOS)
DAY	-45	-15	1	15	22	29	36	46
WINDOW (DAYS)	≤45d prior to Visit 3	≥15d prior to Visit 3	14d±2d from Visit 2	14d±2d from Visit 3	21d±2d from Visit 3	28d±2d from Visit 3	7d±2d from Visit 6	10d±1d from Visit 7
Informed Consent/Assent a	$X^b$							
R-MOAS Scale	X	X	X	X	X	X	X	X
MINI-KID & Vitiello Aggression Scales	X							
Medical History	X		X c					
Demographics	X							
Physical Examination & ECG (12-lead)	X						X	
Inclusion/Exclusion Criteria	X		$X^d$					
Randomization			$X^{b}$					
Urine Drug Screen	X	X	X	X	X	X	X	X
Pregnancy Test e	$X^{f}$	X	X	X	X	X	X	X
Diary Training & Distribution or Evaluation		X	$X^{g}$	X	X	X	X	
Vital Signs h	X		X	X	X	X	X	X
Weight, Height, BMI	X		X			X		X
Hematology/Chemistry/U rinalysis	X		X				X	X
PK Blood Sampling i					X	X		
PGx sampling 	X							

Version 2 Page **7** of **16 11/29/2023** 

a. Written consent must be obtained prior to performing any study-related procedure.

	1	1 0	<del>, ,</del>	1				
Columbia Suicide Severity Rating Scale (CSSRS)	X		X	X	X	X	X	X
Caregiver and Investigator CGI-S	$X^{j}$		X	X	X	X	X	
Caregiver and Investigator CGI-I				X	X	X	X	
SNAP-IV, CHQ-PF28, SIPA			X				X	
Infrequent Behaviors Checklist		X k	X	X	X	X	X	
Simpson-Angus, Barnes & AIMS			X	X	X	X	X	X
Adverse Events			X	X	X	X	X	X
Concomitant Medications	X	X	X	X	X	X	X	X
Drug Dispensation			X b	X	X	X	X	
Drug Return and Compliance				X	X	X	X	X
Diary Return				-				X

- b. Subject number will be assigned via
- c. Assess for any clinically significant change in Medical History since screening.
- d. Confirm inclusion/exclusion criteria.
- e. Urine pregnancy test will be performed for all female subjects. Prior to the administration of the first dose of SM subjects will have to be tested as negative to continue in the study. If Visit 1 and Visit 2 occur on the same day then both urine and serum pregnancy tests must be performed.
- f. Serum pregnancy test will be performed at Screening for all female subjects.
- g. Diary compliance must be at least 70% (minimum of 11 days out of 15) to qualify for randomization.
- h. Heart Rate (HR), blood pressure (BP), temperature, and respiratory rate will be measured.
- i. PK blood samples will be obtained over two visits
- j. Only the Investigator-rated CGI-S will be completed at Screening; Caregiver and Investigator-rated CGI-S will be collected at randomization and every visit thereafter.
- k. The checklist will be recorded on a paper source and entered on EDC only at Visit 2.
- 1. Optional

## **4.2** Sample Size and Power Consideration

Assuming a mean difference of 15 between SPN-810 dose group and placebo with a common standard deviation of 35, a sample of 93 subjects per arm will yield 80 % power to detect a non-zero difference between the median of SPN-810 treatment group and the placebo group using the Wilcoxon rank-sum test with a 2-sided significance level  $\alpha$ =0.05.

### **5 STATISTICAL METHODS and ANALYSES**

#### **5.1** General Considerations

Because SPN-810 did not show efficacy for the Treatment of Impulsive Aggression in the two previous Double-Blind Studies (810P301 and 810P302), the conduct of this study (810P503) was halted. Therefore, the analysis will be limited to the primary, key secondary endpoints and safety data, which will include adverse events (AEs), Extrapyramidal Symptoms (EPS), Simpson-Angus Scale, Barnes Akathisia Scale, and Abnormal Involuntary Movement Scale, clinical laboratory evaluations, vital signs, suicidal symptoms (C-SSRS) and ECG results.

All descriptive statistical analyses will be performed using SAS (Version 9.4), unless otherwise noted and will be presented by treatment groups (Placebo, SPN-810).

Continuous variable summaries will include the number of subjects (n) with non-missing values, mean, standard deviation (SD), median, interquartile range (Q1 and Q3), minimum, and maximum.

Categorical variable summaries will include the frequency and percentage of subjects who are in the category or each possible value. In general, the denominator for the percentage calculation will be based upon the total number of subjects in the study population for the treatment groups, unless otherwise specified. The denominator for by visit displays will be the number of subjects in the relevant study population with non-missing data at each study visit.

In general, the baseline value for a variable is defined as the last observation prior to the first dose of double-blind study medication, ideally Visit 3, but including the screening value, if necessary.

All data will be presented in Listings.

# **5.2** Analysis Population

The population of "all enrolled subjects" consists of all those screened subjects who meet the requirements for study participation and are entered in the Baseline period of the study. The population of "all randomized subjects" consists of all those enrolled subjects who complete the Baseline Period, meet the inclusion/exclusion criteria and are randomized via the The safety population will include all subjects who received at least 1 dose of study drug and has at least one post-baseline safety assessment.

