1. Cross-validation of the electronic impulsive aggression (IA) Diary in adolescents;

2.

3. Pharmacogenomics (PGx).

Study Design: This is a double-blind, randomized, parallel group, two-arm, placebo-controlled study with flexible dosing (36, 45 or 54 mg/day) of SPN-810. Subjects will be randomized to the two arms in 1:1 ratio of SPN-810 or placebo.

Number of Subjects: Approximately 372 subjects aged 12-17 years (inclusive) will be screened to randomize approximately 186 subjects; 93 in the SPN-810 arm, 93 in the placebo arm.

The sample size for the trial may be revised after the results of the ongoing 810P301 and 810P302 studies become available.

Key Criteria for Inclusion:

Otherwise, healthy non-smoking, male and females adolescents (12-17 years of age at the time of screening) with a primary diagnosis of ADHD and currently taking an optimized FDA-approved ADHD medication. IA will be confirmed at screening using R-MOAS scale and Vitiello Aggression Questionnaire.

Key Criteria for Exclusion:

History or current diagnosis of epilepsy, major depressive disorder, bipolar disorder, schizophrenia and other psychotic disorders, personality disorder, Tourette's syndrome or dissociative disorder, autism spectrum disorder, pervasive developmental disorder, obsessive compulsive disorder, post-traumatic stress disorder, or intermittent explosive disorder. Known or suspected intelligence quotient (IQ) <70, active suicidal plan/intent or active suicidal thought, criminal arrest, alcohol or drug use or pregnancy.

Treatment, Dose, and Mode of Administration:

Molindone hydrochloride extended-release tablet dosage forms of 3 mg and 9 mg with matching placebo tablets. Treatment to be administered orally twice daily with or without food. Subjects will be force-titrated over a period of 2 weeks to 36 mg/day.

- Treatment 1: Placebo
- Treatment 2: Flexible dose of SPN-810 titrated to 36 mg, 45 mg, or 54 mg

Duration of Treatment and Study Duration:

Total duration of study: Approximately 13 weeks

- Pre-treatment Phase: Up to 45 days
 - Screening period: Up to 30 days
 - Baseline period: At least 15 days
- Treatment Phase: 36 days
 - Titration period: 2 weeks
 - Maintenance period: 3 weeks

Conversion/taper Phase: 10 days

Pre-Treatment Phase:

Screening and Baseline

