4.3.2 Treatment Phase: (2-5 weeks)

4.3.2.1 Titration period (2 weeks), Day 1 to Day 14

Inclusion/exclusion criteria will be re-assessed to verify eligibility prior to study randomization at the end of Visit 3. Eligible subjects will be randomized at Visit 3 (Day 1) in a 1: 1 ratio to receive 36 mg/day SPN-810 or placebo and proceed to the two-week Titration period in order to reach the maintenance dose of 36 mg/day over a period of 2 weeks.

4.3.2.2 Flexible Maintenance period (3 weeks), Day 15 to Day 35

Following dose titration, all subjects will remain at the reached dose of SPN-810 (36 mg/day) or placebo on the first week of the Maintenance period. After the first week, the Investigator will clinically assess whether to increase the dose to 45 mg/day SPN-810 or placebo, or remain at 36 mg/day of SPN-810 or placebo. On the following week, the Investigator will re-assess the dosage: the subject may remain at 36 mg/day or 45 mg/day or matching placebo (depending on the dosage from the previous week) or titrate up to the higher dose of 45 mg/day or 54 mg/day of SPN-810 or placebo, respectively. Dose reduction will also be allowed during the second week of the Maintenance period in consultation with the Medical Monitor and the Sponsor; at Visit 6 the Investigator may adjust the dose based upon tolerability.

4.3.3 Conversion Phase (10 days), Day 36 to day 45

At the end of the 3-week Maintenance period (Visit 7), subjects will enter a 10 day Conversion Phase if the subject chooses to enroll into an ongoing open-label extension (OLE) study (i.e., 810P304). A blinded double-dummy conversion card will be distributed to down or up-titrate

This document is confidential. It contains proprietary information of Supernus[®] Pharmaceuticals, Inc. Any viewing or disclosure of such information that is not authorized in writing by the Sponsor is strictly prohibited. Such information may be used solely for the purpose of reviewing or performing this study.

CONFIDENTIAL Version 3

the study medication and matching placebo. Subjects will return to the study site for a final end-of-study (EOS) visit, (Visit 8), after completing the Conversion Phase (Figure 1).

4.3.4 Taper Phase (10 days), Day 36 to day 45

At Visit 7, subjects who opt to discontinue from the study will receive a blinded taper card to titrate down the study medication. At the completion of the Taper Phase, subjects will return to the study site to complete the EOS procedures (Figure 2).

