5.3.2 Baseline/ Visit 2, Day -15

Visit 2 will occur at least 15 days prior to Visit 3 as per the Schedule of Events and Procedures.

- 1. Administer R-MOAS scale
- 2. Collect urine for drug screen and pregnancy test (If Visit 1 and Visit 2 occur on the same day then both urine and serum pregnancy tests must be performed)
- 3. Conduct training for the electronic IA diary
- 4. Distribution of IA diary

- 5. Record Infrequent IA Behaviors
- 6. Record and assess concomitant medications

5.3.3 Visit 3, Day 1

Visit 3 will occur at least 14 days (±2 days) following Visit 2 as per the Schedule of Events and Procedures.

- 1. Administer R-MOAS scale
- 2. Assessment for any clinically significant changes in medical history
- 3. Confirm eligibility to randomize subject
- 4. Assess IA diary compliance/review training as necessary
- 5. Randomize subject
- 6. Collect urine sample for drug screen, urinalysis and pregnancy test
- 7. Record weight, height and BMI
- 8. Record vital signs (HR, BP, temperature, and RR)
- 9. Collect blood samples for hematology and chemistry
- 10. Administer Columbia Suicide Severity Rating Scale (C-SSRS)
- 11. Administer Caregiver and Investigator-completed CGI-S scale
- 12. Administer SNAP-IV, CHQ-PF 28 and SIPA scales
- 13. Administer safety scales (Simpson-Angus, Barnes-Akathisia, AIMS)
- 14. Record adverse events
- 15. Record Infrequent IA Behaviors
- 16. Record concomitant medications
- 17. Dispense SM via I

5.3.4 Visit 4, Day 15

Visit 4 will occur 14 days (±2 days) following Visit 3 according to the Schedule of Visits and Procedures.

- 1. Administer R-MOAS scale
- 2. Review IA diary compliance and provide training as needed
- 3. Record dosing diary compliance and provide training as needed
- 4. Collect urine sample for pregnancy test and drug screen
- 5. Record vital signs (HR, BP, temperature, and RR)
- 6. Administer Columbia Suicide Severity Rating Scale (C-SSRS)
- 7. Administer Caregiver and Investigator-completed CGI-S scale
- 8. Administer Caregiver and Investigator- completed CGI-I scale
- 9. Administer safety scales (Simpson-Angus, Barnes-Akathisia, AIMS)
- 10. Record adverse events
- 11. Record Infrequent IA Behaviors
- 12. Record concomitant medications
- 13. Collect returned SM assess treatment compliance

14. Dispense SM

5.3.5 Visit 5, Day 22

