8.3 Analysis Populations

The population of "all enrolled subjects" consists of all those screened subjects who meet the requirements for study participation and are entered in the Baseline period of the study. The population of "all randomized subjects" consists of all those enrolled subjects who complete the Baseline Period, meet the inclusion/exclusion criteria and are randomized.

Safety Population: will include all subjects who received at least 1 dose of study drug and had at least one post-baseline safety assessment.

Full Analysis Set (FAS): will include all screened subjects who received at least 1 dose of study drug and have completed baseline and at least 1 valid post-randomization assessment of frequency of IA behaviors based on IA diary entry.

Per-Protocol (PP) Population: will include all subjects who completed Treatment Phase and did not have major protocol deviations (as defined in the SAP).

PK population: will include all subjects in the safety population who have received at least 1 dose of study drug and had one PK sample drawn which had quantifiable concentration for molindone.

The safety, psychometric, FAS, PP, and PK populations are based on randomized treatment received.

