9.5 Safety Analysis

Evaluation of safety will be performed for the safety population. Safety data that will be evaluated include concomitant medications, AEs, clinical laboratory results, vital signs, ECGs, and findings from the physical examinations. The occurrence of neurological side effects will be assessed by looking at any worsening in scores from Visit 3 to each subsequent visit for each of the Simpson-Angus scale, Barnes Akathisia scale, and AIMS. Suicidal ideation and suicidal behavior will be measured by C-SSRS.

All summary tables related to safety analyses will use the safety population.

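### The safety population drops dosed subjects who have no post-baseline safety assessment, so adverse-event rates are not on an all-treated denominator; the group affected is narrow and may be empty

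*SAP*

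**What the plan says.** SAP 5.2 defines the set with two conditions, a dose and a later assessment: "The safety population will include all subjects who received at least 1 dose of study drug and has at least one post-baseline safety assessment". Protocol 8.3 matches it; its safety population "will include all subjects who received at least 1 dose of study drug and had at least one post-baseline safety assessment".

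The set determines the published percentages. Protocol 9.5: "All summary tables related to safety analyses will use the safety population". SAP 5.1 adds that, in general, "the denominator for the percentage calculation will be based upon the total number of subjects in the study population for the treatment groups". SAP 7 names no other population for adverse events.

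On timing, the Protocol synopsis says: "Subjects will be force-titrated over a period of 2 weeks to 36 mg/day". Protocol 4.3.2.1 is headed "Titration period (2 weeks), Day 1 to Day 14". The next routine visit after Day 1 is set in Protocol 5.3.4: "Visit 4 will occur 14 days (±2 days) following Visit 3 according to the Schedule of Visits and Procedures".

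Four other provisions bear on who is affected:

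- Protocol 4.3.6, 5.3.8 and 5.7 send anyone who stops before Visit 4 to a final visit about a week after stopping. Its procedures (5.3.8) include adverse events, vital signs, laboratory tests, the C-SSRS and the three movement-disorder scales.
- Protocol 5.2 allows unscheduled visits in all periods and asks subjects to telephone the site about problems between visits.
- Protocol 6.4 describes safety assessment as including the recording of adverse events at visits.
- SAP 5.3 tabulates the numbers dosed and discontinued early, with loss to follow-up among the reasons. SAP 5.1 promises listings of all data.

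**The concern.** A safety set is normally everyone exposed. Adding a condition that is met only after exposure means a subject can take the drug, stop, not come back, and leave the denominator. If stopping and not returning is related to tolerability, and differs between arms, the comparison of harms is no longer between the groups as treated.

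The point matters more because two weeks of forced dose increases pass before the first routine visit, and because events can reach the database without a visit. Serious events must be reported within 24 hours of the site becoming aware of them (Protocol 6.4.3.1). Extrapyramidal events and neuroleptic malignant syndrome have their own form (6.4.3.2). An event telephoned in on Day 6 meets the treatment-emergent definition in 6.4.2.2. Whether that telephone report also places the subject in the safety population is not stated.

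**Working it through.** **1. The plan's own figures.** Neither document gives a number of dosed subjects without a later safety assessment, so there is no such figure to reproduce. The illustration borrows only the planned 93 per arm. That figure does reproduce with Noether's formula for the Wilcoxon test: P(X<Y) = Φ(15/(35√2)) = 0.619, and n per arm = (1.960 + 0.842)² / (6 × 0.119²) ≈ 92.3, rounded up to 93. SAP 5.1 says the study was halted, so 93 is a planned arm size only.

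**2. Who the clause removes.** Visit 3 is Day 1, so Visit 4 falls on Day 1 + 14 ± 2, that is Day 13 to 17. A subject who stops on Day d before Visit 4 is due at the final visit by about Day d + 7. A stop on Day 5 gives about Day 12, and any stop before Day 8 gives a visit before Day 15.

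| Path after the first dose | In the safety population? |
|---|---|
| Attends Visit 4 | Yes |
| Stops early, attends the final visit | Yes |
| Attends an unscheduled visit where safety is assessed | Yes |
| Telephones in an event, never attends | Unclear |
| No contact at all | No |

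Only the last two rows are at issue.

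**3. Effect on a displayed rate.** Let N be dosed subjects in an arm, e those with a recorded event, k those excluded, and x the excluded subjects who had a recorded event. The all-treated rate is e/N and the displayed rate is (e − x)/(N − k). The two bounds are x = k and x = 0. Take N = 93 and e = 28, so e/N = 30.1%; e and k are assumptions.

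| k | All excluded had an event | None had an event |
|---|---|---|
| 0 | 28/93 = 30.1% | 28/93 = 30.1% |
| 1 | 27/92 = 29.3% | 28/92 = 30.4% |
| 2 | 26/91 = 28.6% | 28/91 = 30.8% |
| 5 | 23/88 = 26.1% | 28/88 = 31.8% |
| 9 | 19/84 = 22.6% | 28/84 = 33.3% |

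For scale, the Protocol 9.3 dropout assumption of about 20% is 0.20 × 93 = 18.6 per arm over the whole study, with no timing given. Nine would be about half of that.

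**4. Direction.** The displayed rate is below the all-treated rate only when x/k exceeds e/N.

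- If a telephone report counts as an assessment, a subject with a recorded event is never excluded. Then x = 0 and the rate can only rise.
- If it does not count, x can exceed 0 and the direction depends on the unknown x/k. With k = 5, x = 1 gives 27/88 = 30.7% (higher) and x = 2 gives 26/88 = 29.5% (lower).

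**The case against.** The strongest reply is that almost nobody is affected. A reader who sees that the first routine visit is at Day 15 might infer that no safety data can exist before then, and that everyone lost during titration vanishes from the tables. The documents do not support that. Early discontinuers are due a final visit with full safety procedures about a week after stopping, unscheduled visits are available, and Visit 4 itself may fall on Day 13, before titration ends. This part of the reply stands and sets the scope of the point.

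Second, the term is not left wholly open. Protocol 6.4 names adverse-event recording as part of safety assessment, so a reading limited to scales, laboratory tests and vital signs is the less natural one. This also stands, and the lower bounds in the table depend on that less natural reading. What remains open is narrower: Protocol 6.4 ties assessment to visits, so a report made only by telephone is not settled.

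Third, the disposition table shows the number dosed, all adverse events are listed, and the SAP's safety summaries are descriptive with no test between arms. A careful reader could therefore find the excluded subjects. That limits concealment but leaves the tabulated percentages as they are.

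Fourth, an all-dosed set counts subjects without follow-up as event-free, which can understate rates. True, but the choice is then visible and applies to both arms, and a footnote shows how many subjects it concerns. Events never reported to anyone are lost under either definition.

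**Conclusion.** The point holds in a narrow form. Both documents make membership of the safety population depend on a post-dosing assessment. A dosed subject who attends no final, unscheduled or Visit 4 assessment can therefore leave the denominator of the adverse-event tables, and possibly the numerator.

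The size is unknown. The documents give no count of such subjects, and if there are none no result changes. The 26.1% to 31.8% range around 30.1% rests on three assumptions: 93 dosed in an arm, 28 with a recorded event, and 5 excluded.

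Two stronger conclusions are tempting and not supported. One is that the clause hides harm on SPN-810: the direction depends on how a telephone report is treated and on the event rate among those excluded, and neither is given. The other is that safety is the main purpose left to the halted study: SAP 5.1 keeps the primary and key secondary endpoints alongside it. This is a cheap improvement to the definition, not evidence of a biased result.

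**What to change.** In SAP 5.2, define the safety population as every subject who took one or more doses of study drug, and delete the post-baseline assessment condition. Use that set as the denominator for the tables of adverse events, serious adverse events, events of special interest and events leading to discontinuation. Add a footnote giving, by arm, the number dosed with no post-dose safety assessment.

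Align Protocol 8.3 for consistency. Protocol 8.1 lets the SAP supersede the protocol's statistical methods, so the SAP edit is the one that governs.

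Nothing else needs to move. By-visit tables keep the non-missing denominator in SAP 5.1. SAP 6, which builds efficacy on this set, keeps its own requirement for sufficient diary data.

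The cost is one deleted clause and one footnote. The downside is that subjects with no follow-up count as having no recorded event, which the footnote makes plain.
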